8.2.2. Abnormal Test Findings

Abnormal objective test findings should be recorded as AEs when any of the following conditions are met:

- Test result is associated with accompanying symptoms; and/or

- Test result requires additional diagnostic testing or medical/surgical intervention; and/or
- Test result leads to a change in study dosing (outside of any protocol-specified dose adjustments) or discontinuation from the study, significant additional concomitant drug treatment, or other therapy; and/or
- Test result is considered to be an AE by the investigator or sponsor.

Merely repeating an abnormal test, in the absence of any of the above conditions, does not constitute an AE. Any abnormal test result that is determined to be an error does not require recording as an AE.

8.2.3. Serious Adverse Events

A serious adverse event is any untoward medical occurrence at any dose that:

- Results in death;
- Is life-threatening (immediate risk of death);
- Requires inpatient hospitalization or prolongation of existing hospitalization;
- Results in persistent or significant disability/incapacity (substantial disruption of the ability to conduct normal life functions);
- Results in congenital anomaly/birth defect.

Or that is considered to be:

- An important medical event.

Medical and scientific judgment is exercised in determining whether an event is an important medical event. An important medical event may not be immediately life-threatening and/or result in death or hospitalization. However, if it is determined that the event may jeopardize the subject or may require intervention to prevent one of the other AE outcomes, the important medical event should be reported as serious.

Examples of such events are intensive treatment in an emergency room or at home for allergic bronchospasm; blood dyscrasias or convulsions that do not result in hospitalization; or development of drug dependency or drug abuse.

8.2.4. Hospitalization

Hospitalization is defined as any initial admission (even less than 24 hours) in a hospital or equivalent healthcare facility, or any prolongation of an existing admission. Admission also includes transfer within the hospital to an acute/intensive care unit (eg, from the psychiatric wing to a medical floor, medical floor to a coronary care unit, or neurological floor to a tuberculosis unit). An emergency room visit does not necessarily constitute a hospitalization; however, the event leading to the emergency room visit is assessed for medical importance.

Hospitalization does not include the following:

- Rehabilitation facilities;
- Hospice facilities;
- Respite care (eg, caregiver relief);
- Skilled nursing facilities;
- Nursing homes;
- Same-day surgeries (as outpatient/same-day/ambulatory procedures).

Hospitalization or prolongation of hospitalization in the absence of a precipitating clinical AE is not in itself an SAE. Examples include:

- Admission for treatment of a preexisting condition not associated with the development of a new AE or with a worsening of the preexisting condition (eg, for workup of a persistent pretreatment laboratory abnormality);
- Social admission (eg, subject has no place to sleep);
- Administrative admission (eg, for yearly physical examination);
- Protocol-specified admission during a study (eg, for a procedure required by the study protocol);
- Optional admission not associated with a precipitating clinical AE (eg, for elective cosmetic surgery);
- Hospitalization for observation without a medical AE;
- Preplanned treatments or surgical procedures. These should be noted in the baseline documentation for the entire protocol and/or for the individual subject.

Diagnostic and therapeutic noninvasive and invasive procedures, such as surgery, should not be reported as SAEs. However, the medical condition for which the procedure was performed should be reported if it meets the definition of an SAE. For example, an acute appendicitis that begins during the reporting period should be reported if the SAE requirements are met, and the resulting appendectomy should be recorded as treatment of the AE.

8.3. Severity Assessment

If required on the AE page of the CRF, the investigator will use the adjectives MILD, MODERATE, or SEVERE to describe the maximum intensity of the AE. For purposes of consistency, these intensity grades are defined as follows:	
MILD	Does not interfere with subject's usual function.
MODERATE	Interferes to some extent with subject's usual function.
SEVERE	Interferes significantly with subject's usual function.

Note the distinction between the severity and the seriousness of an AE. A severe event is not necessarily an SAE. For example, a headache may be severe (interferes significantly with the subject's usual function) but would not be classified as serious unless it met one of the criteria for SAEs, listed above.

8.4. Special Situations

8.4.1. Protocol-Specified Serious Adverse Events

There are no protocol-specified SAEs in this study. All SAEs will be reported to Pfizer Safety by the investigator as described in previous sections, and will be handled as SAEs in the safety database.

8.4.2. Potential Cases of Drug-Induced Liver Injury

Humans exposed to a drug who show no sign of liver injury (as determined by elevations in transaminases) are termed “tolerators,” while those who show transient liver injury, but adapt are termed “adaptors.” In some subjects, transaminase elevations are a harbinger of a more serious potential outcome. These subjects fail to adapt and therefore are “susceptible” to progressive and serious liver injury, commonly referred to as drug-induced liver injury (DILI). Subjects who experience a transaminase elevation above 3 times the upper limit of normal (\times ULN) should be monitored more frequently to determine if they are an “adaptor” or are “susceptible.”

In the majority of DILI cases, elevations in aspartate aminotransferase (AST) and/or alanine aminotransferase (ALT) precede total bilirubin (TBili) elevations ($>2 \times$ ULN) by several days or weeks. The increase in TBili typically occurs while AST/ALT is/are still elevated above $3 \times$ ULN (ie, AST/ALT and TBili values will be elevated within the same lab sample). In rare instances, by the time TBili elevations are detected, AST/ALT values might have decreased. This occurrence is still regarded as a potential DILI. Therefore, abnormal elevations in either AST OR ALT in addition to TBili that meet the criteria outlined below are considered potential DILI (assessed per Hy’s law criteria) cases and should always be considered important medical events, even before all other possible causes of liver injury have been excluded.

The threshold of laboratory abnormalities for a potential DILI case depends on the subject's individual baseline values and underlying conditions. Subjects who present with the following laboratory abnormalities should be evaluated further as potential DILI (Hy's law) cases to definitively determine the etiology of the abnormal laboratory values:

- Subjects with AST/ALT and TBili baseline values within the normal range who subsequently present with AST OR ALT values $>3 \times \text{ULN}$ AND a TBili value $>2 \times \text{ULN}$ with no evidence of hemolysis and an alkaline phosphatase value $<2 \times \text{ULN}$ or not available;
- For subjects with baseline AST **OR** ALT **OR** TBili values above the ULN, the following threshold values are used in the definition mentioned above, as needed, depending on which values are above the ULN at baseline:
 - Preexisting AST or ALT baseline values above the normal range: AST or ALT values >2 times the baseline values AND $>3 \times \text{ULN}$; or $>8 \times \text{ULN}$ (whichever is smaller).
 - Preexisting values of TBili above the normal range: TBili level increased from baseline value by an amount of at least $1 \times \text{ULN}$ **or** if the value reaches $>3 \times \text{ULN}$ (whichever is smaller).

Rises in AST/ALT and TBili separated by more than a few weeks should be assessed individually based on clinical judgment; any case where uncertainty remains as to whether it represents a potential Hy's law case should be reviewed with the sponsor.

The subject should return to the investigator site and be evaluated as soon as possible, preferably within 48 hours from awareness of the abnormal results. This evaluation should include laboratory tests, detailed history, and physical assessment.

In addition to repeating measurements of AST and ALT and TBili, laboratory tests should include albumin, creatine kinase (CK), direct and indirect bilirubin, gamma-glutamyl transferase (GGT), prothrombin time (PT)/international normalized ratio (INR), total bile acids, alkaline phosphatase and acetaminophen drug and/or protein adduct levels. Consideration should also be given to drawing a separate tube of clotted blood and an anticoagulated tube of blood for further testing, as needed, for further contemporaneous analyses at the time of the recognized initial abnormalities to determine etiology. A detailed history, including relevant information, such as review of ethanol, acetaminophen (either by itself or as a coformulated product in prescription or over-the-counter medications), recreational drug, supplement (herbal) use and consumption, family history, sexual history, travel history, history of contact with a jaundiced person, surgery, blood transfusion, history of liver or allergic disease, and potential occupational exposure to chemicals, should be collected. Further testing for acute hepatitis A, B, C, D, and E infection and liver imaging (eg, biliary tract) may be warranted.

All cases demonstrated on repeat testing as meeting the laboratory criteria of AST/ALT and TBili elevation defined above should be considered potential DILI (Hy's law) cases if no other reason for the LFT abnormalities has yet been found. **Such potential DILI (Hy's law) cases are to be reported as SAEs, irrespective of availability of all the results of the investigations performed to determine etiology of the LFT abnormalities.**

A potential DILI (Hy's law) case becomes a confirmed case only after all results of reasonable investigations have been received and have excluded an alternative etiology.

8.4.3. Exposure to the Investigational Product During Pregnancy or Breastfeeding, and Occupational Exposure

Exposure to the investigational product under study during pregnancy or breastfeeding and occupational exposure are reportable to Pfizer Safety within 24 hours of investigator awareness.

8.4.3.1. Exposure During Pregnancy

For both unapproved/unlicensed products and for marketed products, an exposure during pregnancy (EDP) occurs if:

- A female becomes, or is found to be, pregnant either while receiving or having been exposed (eg, because of treatment or environmental exposure) to the investigational product; or the female becomes or is found to be pregnant after discontinuing and/or being exposed to the investigational product;
- An example of environmental exposure would be a case involving direct contact with a Pfizer product in a pregnant woman (eg, a nurse reports that she is pregnant and has been exposed to chemotherapeutic products).
- A male has been exposed (eg, because of treatment or environmental exposure) to the investigational product prior to or around the time of conception and/or is exposed during his partner's pregnancy.

If a subject or subject's partner becomes or is found to be pregnant during the subject's treatment with the investigational product, the investigator must report this information to Pfizer Safety on the CT SAE Report Form and an EDP supplemental form, regardless of whether an SAE has occurred. In addition, the investigator must submit information regarding environmental exposure to a Pfizer product in a pregnant woman (eg, a subject reports that she is pregnant and has been exposed to a cytotoxic product by inhalation or spillage) to Pfizer Safety using the EDP supplemental form. This must be done irrespective of whether an AE has occurred and within 24 hours of awareness of the exposure. The information submitted should include the anticipated date of delivery (see below for information related to termination of pregnancy).

Follow-up is conducted to obtain general information on the pregnancy and its outcome for all EDP reports with an unknown outcome. The investigator will follow the pregnancy until completion (or until pregnancy termination) and notify Pfizer Safety of the outcome as a follow-up to the initial EDP supplemental form. In the case of a live birth, the structural integrity of the neonate can be assessed at the time of birth. In the event of a termination, the

reason(s) for termination should be specified and, if clinically possible, the structural integrity of the terminated fetus should be assessed by gross visual inspection (unless pre-procedure test findings are conclusive for a congenital anomaly and the findings are reported).

If the outcome of the pregnancy meets the criteria for an SAE (ie, ectopic pregnancy, spontaneous abortion, intrauterine fetal demise, neonatal death, or congenital anomaly [in a live-born baby, a terminated fetus, an intrauterine fetal demise, or a neonatal death]), the investigator should follow the procedures for reporting SAEs.

Additional information about pregnancy outcomes that are reported to Pfizer Safety as SAEs follows:

- Spontaneous abortion includes miscarriage and missed abortion;
- Neonatal deaths that occur within 1 month of birth should be reported, without regard to causality, as SAEs. In addition, infant deaths after 1 month should be reported as SAEs when the investigator assesses the infant death as related or possibly related to exposure to the investigational product.

Additional information regarding the EDP may be requested by the sponsor. Further follow-up of birth outcomes will be handled on a case-by-case basis (eg, follow-up on preterm infants to identify developmental delays). In the case of paternal exposure, the investigator will provide the subject with the Pregnant Partner Release of Information Form to deliver to his partner. The investigator must document in the source documents that the subject was given the Pregnant Partner Release of Information Form to provide to his partner.

8.4.3.2. Exposure During Breastfeeding

Scenarios of exposure during breastfeeding must be reported, irrespective of the presence of an associated SAE, to Pfizer Safety within 24 hours of the investigator's awareness, using the CT SAE Report Form. An exposure during breastfeeding report is not created when a Pfizer drug specifically approved for use in breastfeeding women (eg, vitamins) is administered in accord with authorized use. However, if the infant experiences an SAE associated with such a drug's administration, the SAE is reported together with the exposure during breastfeeding.

8.4.3.3. Occupational Exposure

An occupational exposure occurs when, during the performance of job duties, a person (whether a healthcare professional or otherwise) gets in unplanned direct contact with the product, which may or may not lead to the occurrence of an AE.

An occupational exposure is reported to Pfizer Safety within 24 hours of the investigator's awareness, using the CT SAE Report Form, regardless of whether there is an associated SAE. Since the information does not pertain to a subject enrolled in the study, the information is not recorded on a CRF; however, a copy of the completed CT SAE Report Form is maintained in the investigator site file.

8.4.4. Medication Errors

Other exposures to the investigational product under study may occur in clinical trial settings, such as medication errors.

Safety Event	Recorded on the CRF	Reported on the CT SAE Report Form to Pfizer Safety Within 24 Hours of Awareness
Medication errors	All (regardless of whether associated with an AE)	Only if associated with an SAE

8.4.4.1. Medication Errors

Medication errors may result from the administration or consumption of the investigational product by the wrong subject, or at the wrong time, or at the wrong dosage strength.

Medication errors include:

- Medication errors involving subject exposure to the investigational product;
- Potential medication errors or uses outside of what is foreseen in the protocol that do or do not involve the participating subject.

Such medication errors occurring to a study participant are to be captured on the medication error page of the CRF, which is a specific version of the AE page.

In the event of a medication dosing error, the sponsor should be notified immediately.

Whether or not the medication error is accompanied by an AE, as determined by the investigator, the medication error is recorded on the medication error page of the CRF and, if applicable, any associated AE(s), serious and non-serious, are recorded on an AE page of the CRF.

Medication errors should be reported to Pfizer Safety within 24 hours on a CT SAE Report Form **only when associated with an SAE**.

9. DATA ANALYSIS/STATISTICAL METHODS

Detailed methodology for summary and statistical analyses of the data collected in this study will be documented in a statistical analysis plan (SAP) that will be maintained by the sponsor. The SAP may modify the plans outlined in the protocol where appropriate; however, any major modifications of the primary endpoint definitions and/or their analyses will also be reflected in a protocol amendment.

The statistical analysis will not include comparison between the PF-06650833 and tofacitinib arms.

9.1. Sample Size Determination

The primary endpoint of the study will be the change from baseline in the simplified disease activity index (SDAI) at 12 weeks. The study will enroll approximately 198 completers allocated as follows:

PF-06650833 400 mg	PF-06650833 200 mg	PF-06650833 60 mg	PF-06650833 20 mg	Tofacitinib 5 mg BID	Placebo
36	36	36	30	30	30

Assuming a 15% dropout rate the study will enroll approximately 230 subjects. Since the use of tofacitinib in this study may be not be acceptable by regulatory authorities/ethics committess in all countries, achieving full randomization into the tofacitinib arm may prove logistically challenging. Since the tofacitinib arm is serving as an active control for the study, enrollment of approximately 20-30 subjects into that arm will be acceptable.

9.2. Efficacy Analysis

Analysis of the Primary Endpoint Primary efficacy analysis will be conducted on SDAI change from baseline at 12 weeks.

Analysis will include data on all PF-06650833 arms and placebo. Data on the 5 mg tofacitinib arm will not be included in the analysis.

The primary analysis will be conducted on intention-to-treat population, defined as all randomized patients who received at least one dose of investigational drug or a placebo. The sensitivity data sets will be outlined in the SAP and will include per-protocol data set.

The primary analysis will assess the posterior distribution of the placebo adjusted SDAI Week 12 changes from baseline for each of four active arms estimated from a Bayesian ANCOVA model adjusting for baseline SDAI score. Placebo adjusted distribution of active arm is defined as distribution of the difference of two random variables: SDAI 12w change from baseline of the given active arm and the placebo (each of them assessed using Bayesian ANCOVA which is equivalent of having treatment indicator as nominal variable in the

model). The sensitivity analysis will include a model with baseline SDAI and TNF exposure as covariates. The distribution means and variances will be reported. Grid plots visualizing the distributions will be presented. The sensitivity analysis will also include models assuming beta-binomial and negative binomial distributions for SDAI score. The same covariate structure will be employed.

The secondary analyses will include pairwise comparison of the four active PF-06650833 arms and the placebo using the ANCOVA models of the same structure. No prior knowledge on placebo will be integrated. The raw and adjusted for multiplicity p-values will be reported. (Multiplicity adjustment will be performed using Hochberg's test). Means and variances of placebo adjusted treatment effects will be reported.

The secondary and sensitivity analysis will also include: ANCOVA models adjusting for SDAI baseline value, nominal treatment indicator, TNF exposure status (models including geography or country effect will also be considered). Fitting parametric monotone models for dose - response estimation after conducting Bayesian predictive checks on monotonicity (3 and 4 parameter E_{\max} models, semiparametric models based on spline fitting); advanced data visualization techniques for statistical results presentations. This will include multivariate parallel coordinate plots representing each patient response across set of variables, correlation plots, density estimates for SDAI score, box-plots for SDAI and DAS score changes. Model fitting will be conducted using model discrimination approach based on AIC and BIC criteria as well as visual assessment of fit and residuals.

Missing values due to a patient dropping from the study for lack of efficacy or adverse event, will be handled by setting the SDAI score to nonresponsive (baseline observation carried forward, BOCF).

Missing values that occur while the patient is still enrolled (eg, due to a protocol deviation where the data were not collected), will be handled by the method of last observation carried forward (LOCF). The most recent data on each SDAI domain will be used for calculating the missing SDAI score.

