5.1. Allocation to Treatment

Allocation of subjects to treatment groups will proceed through the use of an interactive response technology (IRT) system (interactive Web-based response [IWR]). The site personnel (study coordinator or specified designee) will be required to enter or select information including but not limited to the user's identification (ID) and password, the protocol number, and the subject number and the date of birth of the subject. The site personnel will then be provided with a treatment assignment and dispensable unit (DU) or container number when drug is being supplied via the IRT system. The IRT system will provide a confirmation report containing the subject number and DU or container number assigned. The confirmation report must be stored in the site's files.

There is a 24-hour-a-day, 365-days-a-year IRT helpdesk available for any questions or issues. The study specific IRT reference manual will provide the contact information and further details on the use of the IRT system.

Note: The IRT is the source of the subject number. The IRT system will provide the subject number at the end of the first IRT subject transaction.

A subject will be randomized to one of 6 treatment sequences: 20 mg PF-06650833 MR tablet QD; 60 mg PF-06650833 MR tablet QD; 200 mg PF-06650833 MR tablet QD; 400 mg PF-06650833 MR tablet QD; tofacitinib 5 mg BID; placebo (for both PF-06650833 and tofacitinib). In those regions in which tofacitinib may not be used as an active control, the tofacitinib cohort (and corresponding placebo allocations) will be eliminated. Randomization will be balanced across the treatment groups with respect to prior exposure to a TNF α inhibitor. Since the use of tofacitinib in this study may not be acceptable by regulatory authorities/ethics committees in all countries, achieving full randomization into the tofacitinib arm may prove logistically challenging. Since the tofacitinib arm is serving as an active control for the study, enrollment of approximately 20-30 subjects into that arm will be acceptable.

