9.4. Randomization

The indicator of prior exposure to anti-TNF treatment will be used as a stratification variable for randomization. The randomization will be stratified with respect to this variable to have equal balance on enrolment of TNF naïve (or TNF exposed) subjects across all arms.

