6.1.2. Sensitivity/Robustness Analyses

There are 3 sets of analyses.

Set 1:

The sensitivity analysis will be based sensitivity prior models on the Bayesian analysis outlined in [Appendix 4](#). The Bayesian analysis will be based on ITT population set.

Set 2:

- Population set
 - ITT;
 - PP.
- Missing data imputation
 - Observed;
 - LOCF.
- ANCOVA (see [Section 5.2.2](#))
 - Baseline SDAI as a covariate;
 - Baseline SDAI and previous anti-TNF use as covariates.

Set 3:

- Population set:
 - ITT;
 - PP.
- Missing data imputation – none (Observed);
- MMRM (see [Section 5.2.2](#)) for analysis of change from baseline in SDAI at Weeks 4, 8, and 12:
 - Baseline SDAI as a covariate;
 - Baseline SDAI and previous anti-TNF use as covariates.

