9. APPENDICES

Appendix 1: Summary of Efficacy Analyses

Primary Efficacy Endpoint	Statistical Method	Missing Data
Change from baseline in SDAI at Week 12	ANCOVA with baseline SDAI as a covariate	Observed
Change from baseline in SDAI at Week 12	ANCOVA with baseline SDAI as a covariate	LOCF
Change from baseline in SDAI at Week 12	ANCOVA with baseline SDAI and anti-TNF use as covariates	Observed
Change from baseline in SDAI at Week 12	ANCOVA with baseline SDAI and anti-TNF use as covariates	LOCF
Change from baseline in SDAI at Week 12	Bayesian analysis of posterior distributions of the SDAI scores and placebo adjusted change from baseline	-

Note: Populations (ITT, PP); Treatment Groups (PF-06650833, placebo)

Secondary Efficacy Endpoints	Statistical Method	Missing Data
SDAI remission and low disease activity scale at Weeks 4, 8, and 12	Normal approximation	Observed
SDAI remission and low disease activity scale at Weeks 4, 8, and 12	Normal approximation	NRI
DAS28-3 (ESR), DAS28-3 (CRP), DAS28 -4 (ESR), and DAS28-4 (CRP) remission and low disease activity scale at Weeks 4, 8, and 12	Normal approximation	Observed
DAS28-3 (ESR), DAS28-3 (CRP), DAS28 -4 (ESR), and DAS28-4 (CRP) remission and low disease activity scale at Weeks 4, 8, and 12	Normal approximation	NRI
Change from baseline in SDAI at Weeks 4, 8, and 12	MMRM	Observed

090177e190fc4501\Approved\Approved On: 27-May-2019 06:05 (GMT)

Secondary Efficacy Endpoints	Statistical Method	Missing Data
Change from baseline in DAS28 (eg, DAS28-3 (ESR), DAS28-3 (CRP), DAS28 -4 (ESR), and DAS28-4 (CRP)) at Weeks 4, 8, and 12	MMRM	Observed
ACR20, ACR50, and ACR70 at Weeks 4, 8, and 12	Normal approximation	Observed
ACR20, ACR50, and ACR70 at Weeks 4, 8, and 12	Normal approximation	NRI
Change from baseline in hsCRP at Weeks 4, 8, and 12	MMRM	Observed
Change from baseline in in the Tender/Painful and Swollen Joint Count (28) at Weeks 4, 8, and 12	MMRM	Observed
Change from baseline in PhGA of Arthritis at Weeks 4, 8, and 12	MMRM	Observed

Note: Populations (ITT); Treatment Groups (PF-06650833 and placebo)

090177e190fc4501\Approved\Approved On: 27-May-2019 06:05 (GMT)

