Appendix 4: Additional Methodology Details

Details of Bayesian analysis of posterior distributions of the SDAI scores

Notations/Definitions

$i = 1, 2, \dots, n$; where n is the total number of patients

x_i^B = Baseline SDAI score for Patient i

x_i^W = Week W SDAI score for Patient i

$y_i = -(x_i^W - x_i^B)$; negative change from baseline SDAI at Week W for Patient i

$I_i^D = \begin{cases} 1, & \text{if Patient } i \text{ received Treatment } D \\ 0, & \text{otherwise.} \end{cases}$

[figure not shown]
$d1, d2, d3$: Dose levels of IRAK – 4

P = Placebo treated group

Primary Model – Bayesian Analysis of Covariance

$$y_i = \mu_P^* I_i^P + \sum_{j=1}^3 (\mu_P^* + \Delta_j^*) I_i^{dj} + \beta(x_i^B - \mu^B) + \varepsilon_i,$$

where $\varepsilon_i \sim N(0, \sigma_\varepsilon^2)$

Data visualization techniques

Table shells of figures displaying the primary endpoint results (see below) will be provided in programming document.

- Distribution of treatment effect *for each* Δ_j^* .
- Display of change from baseline by treatment group based on Bayesian Analysis of Covariance.
- Display of change from baseline by treatment group based on Bayesian Analysis of Covariance vs baseline SDAI.

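### The Bayesian ANCOVA used for the primary and interim analyses leaves out the anti-TNF stratification factor, and the visible SAP does not list the TNF-adjusted Bayesian sensitivity model that Protocol 9.2 plans

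*Protocol*

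**What the plan says.** **Stratification.** Protocol 9.4: "The indicator of prior exposure to anti-TNF treatment will be used as a stratification variable for randomization". Protocol 5.1 agrees. The Statistical Methods part of the Protocol Summary instead describes the factor as prior exposure combined with inadequate response.

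**Primary model.** Under Protocol 9.2 the placebo-adjusted Week 12 changes are "estimated from a Bayesian ANCOVA model adjusting for baseline SDAI score". The equation in SAP Appendix 4, under "Primary Model – Bayesian Analysis of Covariance", has treatment terms and centred baseline SDAI, and no stratum term. SAP 5.1 judges separation from placebo on the posterior probability that the effect exceeds zero, without a numeric cut-off. SAP 7 uses the same framework, with a noninformative placebo prior, for a futility rule (below 10% in all active arms) that may be applied but need not be.

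**Adjusted analyses.** Directly after the Bayesian model, Protocol 9.2 adds: "The sensitivity analysis will include a model with baseline SDAI and TNF exposure as covariates". It then says that the distribution means and variances will be reported. In SAP 6.1.2, Set 1 reads "The sensitivity analysis will be based sensitivity prior models on the Bayesian analysis outlined in" Appendix 4. Sets 2 (ANCOVA) and 3 (MMRM) carry the option "Baseline SDAI and previous anti-TNF use as covariates". SAP Appendix 1 repeats it as "ANCOVA with baseline SDAI and anti-TNF use as covariates". SAP 6.5 adds SDAI summaries by previous anti-TNF use.

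**The concern.** When randomisation is stratified, the arms are balanced on the stratum by design. If the stratum also predicts the outcome after baseline adjustment, a model without it leaves the between-stratum variance in the residual. The reported posterior is then wider than the design warrants. Here that model supplies the two posterior probabilities on which the plan relies, for separation from placebo and for futility. The plan already treats the factor as worth adjusting for in its ANCOVA and MMRM analyses.

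At stake are a little precision, a futility probability pulled slightly towards 50%, and a mismatch between the protocol's sensitivity plan and the visible SAP list.

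**Working it through.** **Inputs from the documents.** Completers by arm (Protocol 9.1): 36 + 36 + 36 + 30 + 30 + 30 = 198. This reproduces the plan's total. At 15% dropout, 198/0.85 = 233 and 198 × 1.15 = 228, both close to the stated 230. Tofacitinib is outside the primary analysis, so N = 198 − 30 = 168. The printed Appendix 4 equation sums over three dose levels. I count the four that SAP 6.1 lists, so residual df0 = 168 − 5 − 1 = 162. Up to 50% of subjects may be TNF-exposed (inclusion criterion 11).

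**Assumed, because the documents give no SD or stratum effect.** Stratum effect g = 0.2 to 0.5 residual SD; exposed share p = 0.5 or 0.3; strata balanced within arms.

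**1. Final analysis, flat prior.** Interval width without the stratum relative to width with it:

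ratio = √[(df0 + N·p(1−p)·g²)/df0] × t(0.975, df0)/t(0.975, df0 − 1)

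- p = 0.5, g = 0.2: √(163.68/162) gives 1.0051.
- p = 0.5, g = 0.5: √(172.5/162) gives 1.0319.
- p = 0.3: 1.0043 and 1.0268.
- All dosed subjects instead of completers (168/0.85 ≈ 198 in these five arms), p = 0.5: 1.0051 and 1.0317.

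At p = 0.5 the variance ratios are 1.0104 and 1.0648. Reported precision is therefore that of 168/1.0104 = 166 or 168/1.0648 = 158 subjects. In simulation (20,000 runs per case) the SD of the estimate was the same with and without the term (0.249 at g = 0.2, 0.247 at g = 0.5). Unadjusted 95% intervals covered 95.0% and 95.8%.

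SAP 5.1 sets no cut-off, so take 0.95 as an illustration, with SE inflation √(1 + p(1−p)g²). One-sided error is 0.0492 to 0.0450 instead of 0.05. Power is 79.8% to 78.6% where the adjusted model has 80%. At g = 0.8, beyond the working range, SE inflation is 7.7% and power 76.3%.

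**2. Interim, noninformative prior.** Half of each arm gives N = 18 + 18 + 18 + 15 + 15 = 84 and df0 = 78. The ratios at p = 0.5 are 1.0052 and 1.0329. An adjusted probability of 10% is reported as Φ(Φ⁻¹(0.10)/ratio) = 10.1% or 10.7%. The chance that all four doses fall below 10%, by numerical integration:

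| True state | Adjusted | Unadjusted, g = 0.2 | Unadjusted, g = 0.5 |
|---|---|---|---|
| No dose effect | 1.10% | 1.07% | 0.96% |
| Every dose 0.25 SD worse than placebo | 7.1% | 7.0% | 6.5% |

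**3. Final analysis, informative placebo prior.** The SAP version history records a prior for placebo response; its parameters are not in the supplied text. Suppose it is worth m = 30 to 100 patients, its source differs from this trial by 30 to 50 points in TNF share, and g = 0.3 to 0.5. With w = m/(m + 30), the shift in the effect is w × g × (difference in share). With k = 1 + p(1−p)g², the reported SE is √[k/36 + k/(m + 30)] and the true SD is √[1/36 + (1−w)²/30 + w²/m]. If exposure lowers response, one-sided error at nominal 0.05 is:

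- 0.003 to 0.031 when the prior's source is less exposed;
- 0.074 to 0.25 when it is more exposed.

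A centred stratum term does not remove this. In the most extreme case (m = 100, 50 points, g = 0.5) the shift is 0.192, the reported SE 0.194 and the true SD 0.188. Error is 1 − Φ[(1.645 × 0.194 − 0.192)/0.188] = 0.25 without the term. With the term (k = 1) it is 1 − Φ(1.645 − 0.192/0.188) = 0.27.

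**The case against.** The strongest reply is that the plan already contains the adjusted Bayesian analysis. Protocol 9.2 places the TNF model right after the Bayesian model and promises distribution means and variances. It introduces the p-value ANCOVAs separately, and later lists an ANCOVA with TNF exposure status, so a frequentist reading would duplicate that item. A posterior mean and variance give P(effect > 0) under a normal posterior. This stands. A reader might infer that no TNF-adjusted posterior is planned anywhere; the protocol does not support that.

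A reader might also infer that the SAP dropped the model. That cannot be shown. The priors that SAP 6.1.2 and SAP 7 place in Appendix 4 are absent from the supplied copy, so other content may be absent too.

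It can also be said that Set 2 covers the point. Under a flat prior it nearly does. The match is not exact, because Set 2 uses observed or LOCF data, while Protocol 9.2 carries baseline forward for dropouts due to lack of efficacy or adverse events. Set 2 is also not stated to apply at the interim.

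Finally, the effect is small and the futility rule is non-binding. That stands, and it makes this a minor point.

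**Conclusion.** The point holds as a minor one. The stratification factor is missing from the model behind the primary and interim posterior probabilities. The TNF-adjusted Bayesian model in Protocol 9.2 does not appear in the visible SAP list.

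For the interim, and for any flat-prior analysis with balanced strata, the omission is conservative. Intervals are about 0.5% to 3.2% too wide at 50% exposed (0.4% to 2.7% at 30%), and futility is met slightly less often. These sizes rest on assumed stratum effects of 0.2 to 0.5 SD. No decision is shown to change.

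A reader might extend the conservative label to the final analysis. The documents do not support that if the placebo prior is informative, because stratification balances TNF exposure between arms, not between this trial and the prior's source. The error can then go either way. Nor do they show that such a mismatch exists, since neither the prior nor its TNF mix is in the supplied text.

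**What to change.** **Preferred.** Add the anti-TNF stratum, as recorded in the randomisation system, to the Appendix 4 model as a centred covariate, γ(tᵢ − mean t), for the final and interim analyses. Match the wording in Protocol 9.2 and keep the baseline-only model as a sensitivity analysis.

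**Minimum.** Leave the primary model alone. List the TNF-adjusted Bayesian model of Protocol 9.2 in SAP 6.1.2 Set 1 and for the interim, and report P(effect > 0) from it.

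**With either.**

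- Check that the placebo prior refers to a population with this trial's TNF mix; the covariate alone does not resolve a mismatch.
- Align the Protocol Summary definition of the factor with Protocol 9.4 and 5.1. Inclusion criterion 11 allows a TNF inhibitor to have been stopped for lack of access, so the two definitions classify some subjects differently.

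**Cost.** No new data, and one of 162 residual degrees of freedom (one of 78 at the interim), which is all that is lost if the strata do not differ. If the primary model changes and the sponsor regards that as major, Protocol 9 and SAP 2 call for a protocol amendment. The minimum option leaves the primary analysis unchanged.
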